	7.2	Reporting Procedures	25
8	STUD	PY OVERSIGHT	26
9	CLIN	ICAL SITE MONITORING	27
10	STAT	ISTICAL CONSIDERATIONS	
	10.1	Study Hypotheses	
	10.2	Sample Size Considerations	
	10.3	Final Analysis Plan	
11	SOUR	CE DOCUMENTS AND ACCESS TO SOURCE DATA/DOCUMENTS	29
12	QUAI	LITY CONTROL AND QUALITY ASSURANCE	
13	ETHI	CS/PROTECTION OF HUMAN SUBJECTS:	31
	13.1	Ethical Standard	31
	13.2	Institutional Review Board	31
	13.3	Informed Consent Process	
	13.4	Exclusion of Women, Minorities, and Children (Special Populations)	
	13.5	Participant Confidentiality	
	13.6	Future Use of Stored Specimens and Other Identifiable Data	
14	DATA	A HANDLING AND RECORD KEEPING	
	14.1	Data Management Responsibilities	
	14.2	Data Capture Methods	
	14.3	Types of Data	
	14.4	Schedule and Content of Reports	
	14.5	Study Records Retention	34
	14.6	Protocol Deviations	34
15	PUBL	ICATION/DATA SHARING POLICY	35
16	LITE	RATURE REFERENCES	
17	QUES	TIONNAIRES	
18	FORM	1S	41

LIST OF ABBREVIATIONS

EPT	Electrical Pulp Test
PBF	Pulpal Blood Flow
LDF	Laser Doppler Flowmeter

PROTOCOL SUMMARY

Title:	Assessment of Tooth Vitality Using Pulse Oximeter
Précis:	The vitality of the pulp is determined according to the hea

lth of the vascular supply not the sensory fibers. Objective diagnostic devices that examine pulpal blood flow, such as pulse oximeter have shown promising results for the assessment of pulp vitality. This could be valuable not only in pulp necrosis but also in diagnosis of inflammatory status of the pulp. If blood flow in teeth is related to symptoms and/or pathology, this would likely have much broader applicability in dentistry, as dentists frequently struggle to answer questions such as "is the pain coming from the tooth or another structure?", and "is the tooth alive or dead". These are very important questions in a wide variety of individuals presenting with acute and chronic orofacial pain. In the present study we will measure pulpal blood flow using pulse oximeter in patients who are already undergoing extractions. Conventional tooth assessments (percussion, palpation, cold, and electrical pulp testing) and pulpal blood flow measurements would be used for teeth that are planned for extraction and also up to 2-5 additional teeth in each participant. We will then look to see whether these clinically measured physiologic indicators of tooth vitality are similar to the histological presentation of the extracted teeth

- **Objectives:** The objective of this study is to evaluate if pulse oximeter measurements are a reliable marker for patient's reported symptoms and/or histological evaluations.
- **Population:** 35 participants

Site: University of Michigan, Ann Arbor MI

Study Duration: 24 months

Subject Participation Visit 1: approximately 45 minutes **Duration:**

Estimated Time to 6 months **Complete Enrollment:**

Schematic of Study Design:

	Study-Rel	ated Procedure
	1)	The researcher will gather information initially by asking if any of the teeth are hurting or sensitive to hot/cold
	2)	Participant will complete self-report questionaries' regarding their history of dental pain
	3)	Existing panoramic radiograph will be reviewed by a member of research team prior to choosing which teeth (less than 10) will be to be tested.
	4)	Blood pressure, and heart rate values recorded at this appointment will be obtained from the medical record by a member of research team prior to the extraction.
	5)	The researcher initially will palpate the gum around selected teeth and record any discomfort
	6)	A plastic clip, pulse oximeter will be placed over the teeth, one at a time, to measure blood flow by measuring the presence of pulse in these teeth for approximately for 15-30 seconds per tooth.
Procedure	7)	The clip will remain on the tooth for additional 2-3 minutes to continually measuring pulse while the following tests are taken place:
		a. Cold Testing: This test is used to assess if the tooth is "dead" or "alive" by measuring sensation of cold from the tooth. A small cotton ball will be sprayed with cold spray (called Endo-Ice) and then placed on the surface of that tooth for approximately 15 seconds or till participant reports any sensation of cold. There would be 30 seconds wait time prior to the next step.
		b. Electrical Pulp Testing: This test is used to assess if the tooth is "dead" or "alive" by measuring sensation of electrical pulses from the tooth. A small probe attached to an electrical pulp testing (EPT) device will be placed on the surface of that tooth for approximately 15 seconds or till participant reports any tingling sensation. There would be 30 seconds wait time prior to the next step.
		c. Percussion Testing: This test is used to assess if the tooth is "dead" or "alive". The end of the mouth mirror is used to gently tap on the tooth surface and record any discomfort. There would be 30 seconds wait time prior to removal of the clip.
	8)	Once the tests above are completed, the plastic clip will be removed from your tooth. The pulse oximeter sensors will be removed from the plastic clip and replace with the LDF sensor. The plastic clip will be placed back over the teeth previously tested to measure the blood flow with the LDF. Blood flow will be measured by the presence of a pulse in each tooth for approximately for 15-30 seconds. Once the measurement is obtained, the plastic clip will be removed from the tooth.
	9)	After obtaining participant's permission, researchers will obtain a de-identified copy of the participants dental radiographs
	10)	After planned extraction is completed by the oral surgery provider, the tooth/teeth from the standard of care procedure will be provided to the researcher for further analysis to determine of the tooth is "alive or dead". This process will occur at the University of Michigan, School Of Dentistry
	Standard	care procedures:
	After com	pletion of the study related procedures, patient's care is transferred to their treating clinician for dental extraction
	Post-Extra	action, Histological Analysis:
	Upon con prepared f paraplast microscop	npletion of extraction, the teeth will be placed in formalin-containing bottle. After formalin fixation, the teeth will be for histological examination using 10% EDTA for demineralization. Following that, the teeth are trimmed, embedded in and cut longitudinally to obtain 6um thick section. The sections will be stained with H&E and examined with a light be. The histological diagnosis is based on the classification used by Seltzer et al. as follows:

KEY ROLES AND CONTACT INFORMATION

Principal	[name], Research Investigator,
Investigator:	Chronic Pain and Fatigue Research Center
	[name]
	[name]
	[name]
	(p) [contact]
	(f) [contact]
	[contact]
Institutions:	University of Michigan
	[name]

1.1 Background Information

The ideal test to assess pulp status in diagnosis of odontogenic source of pain should provide a simple, objective, standardized, reproducible, non-painful, non-injurious, accurate, and inexpensive way of assessing the condition of the pulp tissue. (Gutmann 2011) With our current subjective measurements for pain assessments, diagnosis and treatment of dental pain in young children and children (any age) with cognitive impairment (CI) is very challenging. Studies have shown that children with cognitive impairments appear to be more likely to experience significant pain on a regular basis than unimpaired children. (Oberlander, O'Donnell et al. 1999, Massaro, Ronfani et al. 2014) In dentistry, self-report of pain is one of the essential tool for pain assessment and identification of origin of the pain. However, non-verbal children either due to young age of CI are unable to self-report reliably and that by itself challenge the clinician to accurately identify the source of pain.

Previous studies have examined non-subjective diagnostic devices such as the pulse oximeter, laser Doppler flowmetry and crown surface temperature change, to assess pulp vitality. Despite their promising results, these techniques has not become incorporated into dental diagnosis standard of care. (Fanibunda 1986, Fanibunda 1986, Schnettler and Wallace 1991, Fratkin, Kenny et al. 1999, Radhakrishnan, Munshi et al. 2002, Gopikrishna, Tinagupta et al. 2007, Jafarzadeh 2009, Anusha, Madhusudhana et al. 2017)

Pulse oximeter has been one of the earliest methods and most studied. The principle of pulse oximeter design is the fact that the arterial component of blood is pulsatile in nature (time varying). The purpose of using pulse oximeter is to measure the percentage of oxygenated hemoglobin (HbO2) to the total hemoglobin (Hb)- total oxygenated and deoxygenated hemoglobin. Therefore, when light is emitted through LED transmission on the human body (eg finger), the amount of light that passes through after attenuation from various tissues, it reaches to veins and arteries and can indirectly indicate pulsatile component which overcome the contact component.

Previous studies have shown the potential application of conventional pulse oximeter for assessment of the presence of dental pulp vascularity using a modified probe for teeth. (Alghaithy and Qualtrough 2017) It also appears that there is a correlation between oxygen saturation of pulpal circulation with systemic blood using pulse oximeter.(Schnettler and Wallace 1991)

Objective diagnostic devices such as pulse oximeter could be valuable not only in pulp necrosis but also in diagnosis of inflammatory status of the pulp. If blood flow in teeth is related to symptoms and/or pathology, this would likely have much broader applicability in dentistry, as dentists frequently struggle to answer questions such as "is the pain coming from the tooth or another structure?", and "is the tooth alive or dead". These are very important questions in a wide variety of individuals presenting with acute and chronic orofacial pain. In the present study we will measure pulpal blood flow using pulse oximeter in patients who are already undergoing extractions. We will then look to see whether these clinically measured physiologic indicators of tooth vitality are similar to the histological presentation of the extracted teeth.

1.2 **Rationale**

The purpose of this study is to assess tooth health by using a pulse oximeter which measures the blood flow within the tooth. We hypothesize that if we can measure both sensation and blood flow in a tooth, we will be able to better determine if the tooth is "alive or dead". In the future, this method may help determine which teeth are diseased and require dental treatments. The objective of the study is to measure sensation as well as blood flow in a tooth, for potential use in dentistry.

Our specific aims are:

Aim - 1: To measure pulpal blood flow using pulse oximeter and laser Doppler Flowmeter (LDF)

Aim - 2: To measure tooth vitality using Cold, Electrical Pulp tester (EPT), percussion and palpation testing

Aim - 3: To assess histological presentation of the pulp the extracted teeth

Aim - 4: To evaluate the relationships between the Aims 1-3 to determine if pulpal blood flow is a reliable indicator of tooth vitality.

1.3 **Potential Risks and Benefits**

1.3.1 Potential Risks

Hand-held pulse oximeter:

The pulse oximeter is a non-invasive diagnostic device intended to measure systematic blood oxygenation and pulse rate. In this study, we will use a portable pulse oximeter (CMS60D) to measure blood flow in the tooth pulp. Clinical decisions will not be based on the results obtained from this test. The signal emitted from the sensor is light, and there is little to no risk associated from the pulse oximeter to human tissue. The pulse oximeter is battery operated and the sensors are isolated in plastic sheaths.

Infection control measures will be implemented for all items entering the oral cavity. The pulse oximeter sensors will be cleaned with disinfecting wipes (Colorox Healthcare Hydrogen Peroxide Cleaner Disinfectant, Colorox Company, Latham, NY) and then individually wrapped with a latex free, translucent, elastic barrier (CurelasticTM, Steri-Shield Products, Las Vegas, NV). The insulated wiring harness that connects the sensors to the body of the pulse oximeter will also be cleaned with disinfecting wipes and then covered with a barrier film (Universal Cover Barrier, Patterson Dental, Saint Paul, MN). A custom made sensor holder will be used to hold the pulse oximeter sensors onto the teeth (see below for additional details). The sensor holder will be cleaned with disinfecting wipes prior to use.

A new set of sensor holder will be used for each individual patient. We will plan to re-use the sensors total of 1-2 times. At each time, then sensors and its connecting wires will be wiped using

alcohol wipe and then covered using protection barrier, "blue tape". After each use, the blue tape would be removed and the sensors and its connectors be wiped again with alcohol

Laser Doppler Flowmeter (LDF):

The laser Doppler Flowmeter is a non-invasive diagnostic device intended to provide measurement of perfusion. This device is similar to pulse oximetry it identifies the number and velocity of blood cells circulating through vasculature. In this study, we will use a portable Laser Doppler Flowmeter, manufactured by Perimed Inc. to measure blood flow in the tooth. Clinical decisions will not be based on the results obtained from this test. According to PeriFlux System 5000 Manual, The PeriFlux PF 5000 Main Unit contains a diode laser emitting continuous divergent radiation. This laser light is transmitted to the PF 5000 LDF Unit(s). The PeriFlux System 5000 is classified in USA as a class 1 laser which covers the lowest risk laser. The biomedical engineering unit qualified this LDF unit in October of 2013 and tagged it with the hospital tag 464212.

The PeriFlux System 5000 laser Doppler measures micro-circulatory blood flow. Laser light is applied to the tissue through fiber optics. The laser light hits moving blood cells in the microvasculature, and this scatters the light and causes the laser light to change frequency due to Doppler shift. The frequency change will depend on the amount of blood cells in the illuminated area and the speed of those blood cells. Part of the laser light is returned to a photo detector in the instrument. The value from the photo detector is electronically processed and the signal is converted into a perfusion rate.

Infection control measures will be implemented for all items entering the oral cavity. The LDF sensors will be cleaned with disinfecting wipes (Colorox Healthcare Hydrogen Peroxide Cleaner Disinfectant, Colorox Company, Latham, NY) and then individually wrapped with a latex free, translucent, elastic barrier (CurelasticTM, Steri-Shield Products, Las Vegas, NV). The insulated wiring harness that connects the sensors to the body of the LDF will also be cleaned with disinfecting wipes and then covered with a barrier film (Universal Cover Barrier, Patterson Dental, Saint Paul, MN). A custom made sensor holder will be used to hold the LDF sensors onto the teeth and/or supporting gingival. The sensor holder will be cleaned with disinfecting wipes prior to use.

A new set of sensor holder will be used for each individual patient. We will plan to re-use the sensors total of 1-2 times. At each time, then sensors and its connecting wires will be wiped using alcohol wipe and then covered using protection barrier, "blue tape". After each use, the blue tape would be removed and the sensors and its connectors be wiped again with alcohol

Pulse oximeter sensor holder:

The sensor holder is designed to hold the sensors securely around the teeth. The sensor holders are designed in various sizes to accommodate variation in dental anatomies. The first iteration of the sensor holder (i.e., "Design-1") is 3D printed using the Form2Lab Printer (see photo on page 42).

The material used is Dental LT Clear Resin (FormsLab, Somerville, MA) as it can produce accurate, biocompatible parts ideal for this application. Dental LT Clear is tested at NAMSA (Chasse sur Rhône, France) and is certified biocompatible (EN-ISO 10993-1:2009/AC:2010).

Design-1 includes external wings for placement of cotton rolls to increase comfort for the patient. The interface between the sensor and the teeth/gingiva is covered with a thick layer (5-8mm) of clear Memosil 2 (Kulzer, Hanau, Germany). We have planned on including this interface for comfort and also to increase the surface area since the conventional pulse oximeter is against skin and muscle and we plan to place it over the tooth. It has round edges and can be additionally supported on the tooth using OpalDam paste (Ultradent Products, South Jordan, UT) to minimize any risk of accidental abrasion on the adjacent soft tissue. The sensor holder will be disinfected in an ethanol solution between each subject.

There is a small chance that a participant may feel slight pressure on their tooth when the clamp is placed or that it might pinch the gingival tissue a little. If this occurs, the clamp will be repositioned or removed and another size clamp will be used. Some participants might experience pressure from the sensor holder around the tooth following the test. If a subject finds any pressures unbearable or intolerable, he or she may ask the operator to stop the test and the pressure will be immediately removed from the tooth.

Dental pain questionnaire:

There is possibility of discomfort associated with being asked personal questions about history of dental and your overall wellbeing. You may refuse to answer any questions on the questionnaire of survey that may be uncomfortable.

Cold testing:

One of the potential risk of cold testing is temporary mild pain or discomfort at the site of testing. If a subject finds the test unbearable or intolerable, he or she may ask the operator to stop the test and the cotton ball will be immediately removed from the tooth.

Electrical Pulp testing (EPT):

One of the potential risk of EPT testing is temporary mild pain or discomfort at the site of testing. If a subject finds the test unbearable or intolerable, he or she may ask the operator to stop the test and the probe will be immediately removed from the tooth.

Percussion:

One of the potential risk of percussion testing is temporary mild pain or discomfort at the site of testing. If a subject finds the test unbearable or intolerable, he or she may ask the operator to stop the test.

1.3.2 Potential Benefits

Participants are not expected to receive any personal benefits from being in this study.

OBJECTIVES

1.4 **Study Objectives**

The purpose of this study is to assess tooth health by using a pulse oximeter which measures the blood flow within the tooth. We hypothesize that if we can measure both sensation and blood flow in a tooth, we will be able to better determine if the tooth is "alive or dead". In the future, this method may help determine which teeth are diseased and require dental treatments.

Our specific aims are:

Aim - 1: To measure pulpal blood flow using pulse oximeter and Laser Doppler Flowmeter

Aim - 2: To measure tooth vitality using Cold, Electrical Pulp tester (EPT) , percussion and palpation testing

Aim - 3: To assess histological presentation of the pulp the extracted teeth

Aim - 4: To evaluate the relationships between the Aims 1-3 to determine if pulpal blood flow is a reliable indicator of tooth vitality.

1.5 **Study Outcome Measures**

Primary Outcomes Measures: Correlation Between Subjective and Objective Measurements of Pulpal Status

- Subjective Measurements Pulpal Status: Conventional pulpal diagnosis using cold test [Endo Ice, Coltene/Whaledent, Cuyahoga Falls, OH, USA] and Electrical Pulp Test -EPT S[Kerr Vitality Scanner, SybronEndo] testing and recorded, along with vertical and lateral percussion and palpation responses. Conventional pulpal diagnosis assessment would be used for teeth that are planned for extraction and additional teeth (10 total) in each participant
- *Objective Measurements Pulpal Status:* Measurements obtained from pulse oximeter gives a series of reading of oxygen saturation level, and pulse. Pulse oximeter measurements would be used for teeth that are planned for extraction and also up to 2-5 additional teeth in each participant

Exploratory Outcomes:

- *Systemic Vital Sign Measurements:* Blood pressure and pulse recording will be obtained from the recorded values from the participant's chart.
- *Histological Assessment of the Extracted Teeth:* Upon completion of extraction, the teeth will be placed in formalin-containing bottle. After formalin fixation, the teeth will be prepared for histological examination using 10% EDTA for demineralization. Following that, the teeth are trimmed, embedded in paraplast and cut longitudinally to obtain 6um thick section. The sections were stained with H&E and examined with a light microscope.

- *Laser Doppler Flowmeter (LDF):* Measurements obtained from LDF pulse oximeter gives a series of reading of blood velocity. LDF measurements would be used for teeth that are planned for extraction and also up to 2-5 additional teeth in each participant

STUDY DESIGN

Standard Care Procedures:

Participants may receive the following treatment procedures whether he/she join this study or not:

- Review of medical and dental history
- Oral examinations
- Dental Procedures (e.g., extractions) planned by his/her oral surgery provider

Study-Related Procedure

- The researcher will gather information initially by asking if any of the teeth are hurting or sensitive to hot/cold
- Participants will complete self-report questionaries' regarding their history of dental pain
- Existing panoramic radiograph will be reviewed by a member of research team prior to choosing which teeth (less than 10) will be to be tested.
- Blood pressure, and heart rate values would be recorded on this appointment from your medical record by a member of research team prior to the extraction.
- The researcher initially will palpate the gum around selected teeth and record any discomfort
- A plastic clip, pulse oximeter will be placed over the teeth, one at a time, to measure blood flow by measuring the presence of pulse in these teeth for approximately for 15-30 seconds.
- The clip will remain on the tooth for additional 2-3 minutes to continually measuring pulse while the following tests are taken place:
 - **Cold Testing**: This test is used to assess if the tooth is "dead" or "alive" by measuring sensation of cold from the tooth. A small cotton ball will be sprayed with cold spray (called Endo-Ice) and then placed on the surface of that tooth for approximately 15 seconds or till participant reports any sensation of cold. There would be 30 seconds wait time prior to the next step.
 - **Electrical Pulp Testing:** This test is used to assess if the tooth is "dead" or "alive" by measuring sensation of electrical pulses from the tooth. A small probe attached to an electrical pulp testing (EPT) device will be placed on the surface of that tooth for approximately 15 seconds or till participant reports any tingling sensation. There would be 30 seconds wait time prior to the next step.
 - **Percussion Testing:** This test is used to assess if the tooth is "dead" or "alive". The end of the mouth mirror is used to gently tap on the tooth surface and record any discomfort. There would be 30 seconds wait time prior to removal of the clip.
 - 0
- Once the tests above are completed, the plastic clip will be removed from your tooth. The pulse oximeter sensors will be removed from the plastic clip and replace with the LDF sensor. The plastic clip will be placed back over the teeth previously tested to measure the blood flow with the LDF. Blood flow will be measured by the presence of a pulse in each tooth for approximately for 15-30 seconds. Once the measurement is obtained, the plastic clip will be removed from the tooth.

- After obtaining participant's permission, researchers will obtain a de-identified copy of the participants dental radiographs
- After planned extraction is completed by the oral surgery provider, the tooth/teeth from the standard of care procedure will be provided to the researcher for further analysis to determine of the tooth is "alive or dead". This process will occur at the University of Michigan School of Dentistry Oral Surgery Clinics.
- Upon completion of extraction, the teeth will be placed in formalin-containing bottle. After formalin fixation, the teeth will be prepared for histological examination using 10% EDTA for demineralization. Following that, the teeth are trimmed, embedded in paraplast and cut longitudinally to obtain 6um thick section. The sections were stained with H&E and examined with a light microscope. The histological diagnosis are based on the classification used by Seltzer et al. as follow:
 - 1. Normal Pulp: Intact, uninflamed pulp
 - 2. Transitional Stage: Intact pulp with scattered inflammatory cells
 - 3. Pulpitis: inflammatory process affecting the coronal and radicular
 - 4. Pulp Necrosis: All pulp tissue is necrotic

STUDY ENROLLMENT AND WITHDRAWAL

1.6 **Subject Inclusion Criteria**

In order to be eligible to participate in this study, you must meet the following criteria:

- 1. Must be a patient of the University of Michigan School of Dentistry Oral Surgery Clinics
- 2. Must be scheduled for at least one tooth extraction at Oral Surgery Clinic
- 3. Must be 18 to 65 years old
- 4. Must be able to understand and willing to cooperate with all study procedures
- 5. Must be able to sign an IRB-approved written consent
- 6. Must have at least two teeth with an intact crown, without any full metallic crown coverage, and/or previous root canal treatments
- 7. Must have no history of spontaneous pain, and/or lingering pain to cold/hot in teeth that are not going to be extracted on that day.
- 8. If one of the teeth mentioned in inclusion #6 is being extracted, be willing to give your extracted tooth/teeth for further analysis to determine of the tooth is "alive or dead"

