1.20 Study Hypotheses

The calculations are based on a comparison of the test results and "true" disease status. The sensitivity, specificity, and positive and negative predictive values of heat and cold application and electrical pulp tests will be calculated. Teeth are grouped into two categories, healthy, true disease (irreversible pulpitis and necrosis). A perfect diagnostic test would always be positive in the presence of disease and negative in the absence of disease. Therefore, sensitivity, specificity, and positive and negative predictive value have been developed to characterize test accuracy and to compute the benefits of test usage. In addition to that, clinical measurements of the extracted teeth will be compared with identification of the true disease by histological evaluation for the pulp status.

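### The primary outcome correlates the oximeter with sensibility tests, so it cannot answer the histology part of the stated objective

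*Combined protocol and SAP*

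**What the plan says.** The Protocol Summary gives the objective as to "evaluate if pulse oximeter measurements are a reliable marker for patient's reported symptoms and/or histological evaluations". The précis there says that vitality depends on the "vascular supply not the sensory fibers", and it closes on histology: "We will then look to see whether these clinically measured physiologic indicators of tooth vitality are similar to the histological presentation". Aim 4 in Section 1.4 is "To evaluate the relationships between the Aims 1-3 to determine if pulpal blood flow is a reliable indicator of tooth vitality"; Aim 3 is the histology.

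Section 1.5 then sets "Primary Outcomes Measures: Correlation Between Subjective and Objective Measurements of Pulpal Status". The subjective side is cold, EPT, percussion and palpation. The objective side is the pulse oximeter. "Histological Assessment of the Extracted Teeth" appears under the exploratory outcomes, next to blood pressure and pulse taken from the chart.

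The two statistical sections differ on what counts as the truth. Section 1.20 says that "clinical measurements of the extracted teeth will be compared with identification of the true disease by histological evaluation for the pulp status". Section 1.22 gives the label of gold standard to cold and EPT and compares the oximeter with them. Section 1.22 also plans to compare clinical pulpal status with histological status, by ANOVA and McNemar's tests.

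**The concern.** The measure that Section 1.20 treats as the truth is absent from the primary outcome. Whatever the correlation turns out to be, it cannot by itself show that the oximeter marks histological status, and it covers only the part of Aim 4 that links Aims 1 and 2.

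The choice of comparator makes this more than a matter of labels. On the protocol's own account the oximeter measures the vascular property that defines vitality, and the sensibility tests measure something else. Where the sensory tests are wrong, a correct oximeter disagrees with them and the correlation falls. Where both err on the same teeth, the correlation rises. At stake is whether the study's headline result can support a statement that the oximeter is a reliable indicator of vitality.

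**Working it through.** No figure in the plan decides this point. The only one nearby, 35 completers in Section 1.21, comes without inputs and cannot be reproduced. The check is therefore a comparison of the sections, followed by two illustrations on stated assumptions.

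1. **Does the symptoms limb cover the primary outcome?** Symptoms are collected by asking whether teeth hurt or are sensitive (Study Design) and by the dental pain questionnaire (Section 1.17). Neither is in the primary outcome. A response elicited by cold or EPT is a test result, not a reported symptom. The limb is touched indirectly at best.

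2. **Does another planned analysis give the missing estimate?** Section 1.20 names sensitivity, specificity and predictive values for heat, cold and electrical tests only. Section 1.22 compares the oximeter with cold and EPT by correlation, chi-square and paired t-tests. Its histology comparison is worded for clinical pulpal status. No section states a sensitivity or specificity of the oximeter against histology.

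3. **How well does a correlation between two tests reflect accuracy?** For two binary tests, phi = (p11 − p1·p2) / √[p1(1−p1)·p2(1−p2)], where p1 and p2 are the proportions positive on each test and p11 is the proportion positive on both. All accuracies and prevalences below are assumptions, because the documents give none.
   - *Perfect oximeter; cold/EPT 80% sensitive and 90% specific; prevalence 30%.* Both positive: 0.30 × 0.80 = 0.24. Cold/EPT positive: 0.24 + 0.70 × 0.10 = 0.31. Both negative: 0.70 × 0.90 = 0.63. Agreement is 0.24 + 0.63 = 87%. Phi = (0.24 − 0.30 × 0.31) / √(0.30 × 0.70 × 0.31 × 0.69) = 0.147/0.212 = 0.69.
   - *Near-perfect oximeter (98%/98%); weak cold test (60%/70%); independent errors; prevalence 40%.* p11 = 0.4 × 0.6 × 0.98 + 0.6 × 0.3 × 0.02 = 0.2388; p1 = 0.42; p2 = 0.404. Phi = (0.2388 − 0.1697)/0.2422 = 0.29. At 20% prevalence it is 0.24.
   - *Two weak tests (60%/70% each); shared errors at half the maximum covariance; prevalence 40%.* p11 = 0.4 × (0.36 + 0.12) + 0.6 × (0.09 + 0.105) = 0.309; p1 = p2 = 0.42. Phi = (0.309 − 0.1764)/0.2436 = 0.54. At 20% prevalence it is 0.53.

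   The size of the correlation thus depends heavily on the comparator and on shared errors, and it can place a poor device above a good one.

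4. **What precision would a histology-based estimate have?** The number of histology teeth is not stated. For illustration, exact 95% intervals are 57% to 98% for 12 of 14 diseased teeth detected (86%), and 63% to 92% for 28 of 35 (80%), the latter if every participant gave one diseased tooth. Both treat teeth as independent.

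**The case against.** The best defence has four parts.

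- **The objective does not name histology alone.** It joins symptoms and histology by and/or, and Section 1.4 hypothesises that sensation and blood flow together will help determine vitality. A reader might infer that histology is the sole target and that the primary outcome is disconnected from the objective. The documents do not support that. The primary outcome is one part of Aim 4, and the gap concerns the histology limb.

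- **Histology is not left unanalysed.** Section 1.22 plans a comparison, and the sentence in Section 1.20 on clinical measurements of extracted teeth could be read to include the oximeter. This stands. What is missing is priority and a named accuracy measure for the oximeter.

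- **The primary outcome is not empty.** A reader might infer that it says nothing about the true pulp state, or that it would count a perfect oximeter as a failure. Neither follows. A comparator with 80% sensitivity and 90% specificity is informative, the first scenario above gives a strong positive correlation, and no section sets a success threshold. The information is indirect.

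- **Keeping histology exploratory can be defended in a study of 35.** Inclusion criterion 8 and Section 1.31 make histology conditional on an eligible tooth being extracted, so some participants may contribute none. It is also unavailable for the additional, non-extracted teeth. This is a fair reason for caution, but it holds only if the objective is worded to match.

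**Conclusion.** The concern holds in a limited form. The objective, Aim 4 and Section 1.20 bring histology into the question. The primary outcome in Section 1.5 leaves it out, and Sections 1.20 and 1.22 name different reference standards. A positive primary result would not address the histology limb, and no other planned analysis states how accurate the oximeter is against histology.

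That conclusion rests on the text alone. The correlations (0.24 to 0.29 for a near-perfect oximeter against a weak comparator, 0.53 to 0.54 for two weak tests with shared errors, 0.69 for a perfect oximeter against a better comparator) rest on assumed accuracies and prevalences. They show that the correlation is an unreliable substitute for accuracy. They do not predict this study's result. The data to be collected remain usable, so this is a change the sponsor should make rather than a fatal flaw.

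**What to change.** Amend Sections 1.5 and 1.22 together:

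- Make the oximeter's sensitivity and specificity against histology in extracted teeth the primary or co-primary outcome. Give 95% confidence intervals that allow for several teeth from one participant, for example by resampling participants.
- Use the disease grouping of Section 1.20 (irreversible pulpitis plus necrosis versus healthy) and map it to the four histology grades in Section 1.15. The mapping must say where the transitional grade belongs and how the pulpitis grade relates to irreversible pulpitis.
- Fix the oximeter cut-off before the data are examined, and say whether it applies to saturation or to presence of a pulse.
- Report cold and EPT against histology on the same teeth as comparator.
- Make the subjective-objective correlation secondary, or the other co-primary.
- In Section 1.22, call cold and EPT a comparator and drop the gold-standard label, so that it agrees with Section 1.20.

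The cost is a protocol amendment with IRB review. No new procedures or data are needed, and no stated power calculation is disturbed, since Section 1.21 gives none. The downside is precision: the estimate rests on eligible extracted teeth only, their number is not stated, and intervals will be wide. The expected number of such teeth should be written down.

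If the sponsor prefers the present primary outcome, the objective must be narrowed to agreement between the oximeter and sensibility tests.
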